## **7.9.4 Safety Analyses**

Safety parameters include monitoring of AEs, TEAEs, physical examination findings, vital sign measurements, laboratory tests, ECG results, visual acuity, slit-lamp biomicroscopy, and IOP.

Safety data will be summarized and listed with no statistical hypothesis testing performed. Continuous variables will be summarized using the mean, the standard deviation, median, minimum value, and maximum value. Categorical variables will be summarized using frequency counts and percentages.

### **7.9.4.1 Adverse Events**

All AEs will be listed and all TEAEs will be summarized. Adverse events will be deemed treatment-emergent if the onset date is on or after the date of first treatment, Day 1. Events that are not treatment emergent will be listed separately and together with all other AEs. Ocular TEAEs will be summarized separately from non-ocular TEAEs. Ocular TEAEs will be summarized for the study eye, the fellow eye, and either/worse eye (eg, a subject will be counted if the given event occurred in either the study or fellow eye. When events are summarized by relationship or severity, the event with the greatest relationship or severity will be used).

Treatment-emergent AEs will be summarized by treatment group, presenting the number and percentage of subjects having a TEAE in each system organ class and having each individual TEAE based on the preferred term. Additionally, TEAEs will be summarized by the number of events per 100 person-years of follow-up. Treatment-emergent AEs will also be tabulated according to intensity and causality. Subjects who experienced multiple TEAEs for a preferred term (PT) will be counted once, similarly for subjects with multiple TEAEs per system organ class (SOC).

Deaths, SAEs, and TEAEs leading to discontinuation of study drug will be listed separately and, if appropriate, summarized by treatment group, SOC, and PT.

The incidence of AEs over time may also be summarized.

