### 1.3 Rationale for Phase 2a Study MT-0814/2-01

Age-related macular degeneration is the leading cause of blindness among adults in North America and Europe, and it is the fourth-leading cause of visual disorders in Japan. Moreover, the prevalence of AMD has increased in recent years, and its incidence is expected to increase further due the continued aging of the world population. In exudative (wet) AMD, CNV formation is induced by the secretion of vascular endothelial growth factor (VEGF), leading to a rapid decrease in visual acuity due to retinal edema and/or bleeding.

The current standard of care for patients with exudative AMD is the administration of anti-VEGF agents (aflibercept or ranibizumab) via an intravitreal injection every 4 to 8 weeks. Treatment with anti-VEGFs has been demonstrated to benefit patients with AMD by maintaining or even improving visual acuity. However, lifetime dosing of anti-VEGF every 1 to 2 months exposes patients to the risk of acquiring infectious diseases from the intravitreal injection procedure. Additionally, the intravitreal injection procedure itself places a severe burden on patients, caregivers, and ophthalmologists.

[REDACTED]

[REDACTED]

[REDACTED]

[REDACTED]

[REDACTED]

[REDACTED]

[REDACTED]

[REDACTED]

[REDACTED]

[REDACTED]

[REDACTED]

[REDACTED]

[REDACTED]

[REDACTED]

As MT-0814 is an investigational drug with a limited safety profile in humans, all subjects receiving MT-0814 will be closely monitored until sufficient exposure in humans is obtained to determine the clinical safety of MT-0814.

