### **4.2.3 Treatment Failure and Initiation of Rescue Therapy**

In case the investigator considers that the ocular condition is worsening to an extent that the subject needs rescue medication, the subject will be considered a treatment failure.

Investigators should discontinue administration of study drug and begin rescue therapy with intravitreal injections of an anti-VEGF agent (aflibercept or ranibizumab) per standard of care if a subject exhibits any of the following:

- Increase in retinal/subretinal hemorrhage or new retinal/subretinal hemorrhage from Screening for which the investigator deems rescue therapy is necessary.
- Emergence of new retinal/subretinal fluid, increase in retinal/subretinal fluid, or cystoid macular edema from Day 1 for which the investigator deems rescue therapy is necessary.
- Decrease in BCVA of  $\geq 10$  letters from Day 1 that is related to disease activity.
- Any other reason that, in the investigator's opinion, requires discontinuation of study drug and initiation of rescue therapy.

All EOT evaluations need to be completed at the time that treatment failure has been declared.

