### **6.2.2.2 Eliciting and Documenting Adverse Events**

Adverse events will be collected and assessed from the time the subject signs the ICF until they exit from the study or 30 days after the last dose of the study drug, whichever is later. Any AE that occurs after the first dose of study drug is considered treatment-emergent.

Serious AEs that occur more than 30 days after exit from the study or 30 days after the last dose of study drug, whichever is later, will be reported to PPD/sponsor, only if the investigator considers them related to study drug.

At every study visit, subjects will be asked a standard nonleading question to elicit any medically related changes in their well-being. They will also be asked if they have been hospitalized, had any accidents, used any new medications, or changed concomitant medication regimens (both prescription and OTC medications).

In addition to subject observations, AEs will be documented from any data collected on the AE page of the eCRF (eg, laboratory test results or physical examination findings) or identified from review of other documents (eg, subject diaries) that are relevant to subject safety.

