## 7.5 Analysis Sets

The following analysis sets will be used in the statistical analyses:

- Full-analysis set (FAS): The FAS will consist of all participants who were randomly assigned to receive double-masked study drug and who have received at least 1 dose of study drug. All analyses using the FAS will group participants according to randomly assigned treatment.
- Per-protocol set (PPS): The PPS will consist of all FAS participants who meet all of the inclusion criteria and none of the exclusion criteria, have at least 75% compliance with study treatment, have not taken any of the prohibited medications listed in Section 5.8.2, and have no significant protocol deviations. Subjects will not be excluded from the PPS if they discontinued treatment due to lack of efficacy or if they have protocol deviations, including unmasking, that are attributable to lack of efficacy. All analyses using the PPS will group participants according to treatment actually received.
- Safety set (SS): The SS will consist of all participants who received any study drug. All analyses using the SS will group participants according to the treatment that is actually received.
- MT-0814 plasma concentration data set: The PK data set will consist of plasma concentration data of samples obtained from all participants who received any active study drug.

The FAS and PPS will be used for the efficacy analysis with the primary population for analysis being the FAS. Safety will be summarized using the SS.

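### No safety table separates study-eye adverse events or person-time before and after the first rescue injection, so drug and injection effects are pooled under the original study treatment

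*Combined protocol and SAP*

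**What the plan says.** **Definition and window.** For analysis, Section 7.9.4.1 says "Adverse events will be deemed treatment-emergent if the onset date is on or after the date of first treatment, Day 1". For data collection, Section 6.2.2.2 says "Any AE that occurs after the first dose of study drug is considered treatment-emergent". Neither has a closing date or a rescue cut-off. Events are collected from consent "until they exit from the study or 30 days after the last dose of the study drug, whichever is later".

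**Tables.** Section 7.9.4.1 plans that "Treatment-emergent AEs will be summarized by treatment group, presenting the number and percentage of subjects having a TEAE in each system organ class", and also that "TEAEs will be summarized by the number of events per 100 person-years of follow-up". Ocular events are shown for the study eye, the fellow eye and either/worse eye. Tables by intensity and causality and a listing of all events are planned; a summary over time is optional. Grouping is set in Section 7.5: "All analyses using the SS will group participants according to the treatment that is actually received".

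**Rescue.** Under Section 4.2.3 the investigator stops study drug and is to "begin rescue therapy with intravitreal injections of an anti-VEGF agent". On the injection itself, Section 1.3 says that lifetime anti-VEGF dosing "exposes patients to the risk of acquiring infectious diseases from the intravitreal injection procedure", and the synopsis names sight-threatening endophthalmitis.

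**Efficacy, for contrast.** Sections 7.9.1 to 7.9.3 replace data after rescue by worst observation carried forward.

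**The concern.** Rescue changes the treatment: one drug is withdrawn, and another is given by a procedure with its own ocular risks. The efficacy sections treat this as a break, and a rule for data after rescue implies that such data are expected. The safety sections have no matching split.

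Unequal rescue is a real possibility, because the proportion rescued and the time to rescue are themselves secondary endpoints (Section 7.3). If placebo is rescued more, injection events raise the placebo column and MT-0814 looks better by comparison. If a dose is rescued more, its column mixes drug and injection effects. Safety is part of the primary objective (Section 2.1), and these descriptive tables are the only planned between-group display of adverse events.

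**Working it through.** **Inputs from the documents.** About 35 subjects at 3:3:1. The arm sizes reproduce Section 3.1: 35 × 3/7 = 15, 35 × 3/7 = 15, 35 × 1/7 = 5. One subject is 100/5 = 20 points on placebo and 100/15 = 6.7 points in an active arm. Scheduled follow-up ends on Day 113 (Table 13–1). There is no stated rescue rate or injection-event rate to reproduce.

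**Assumptions.** b is the background risk of any ocular event, equal in all arms. r is the proportion rescued. q is the risk of an injection-related ocular event once rescued, independent of b.

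**Formula.** P(at least one ocular event) = 1 − (1 − b)(1 − r·q). The active-minus-placebo difference is therefore (1 − b)·q·(r_active − r_placebo). The true drug effect is set to zero, so any gap comes from rescue alone.

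**Results with b = 10%.**
- Rescue 40% placebo, 20% active, q = 10%: 13.6% versus 11.8%; difference 0.9 × 0.1 × (0.2 − 0.4) = −1.8 points.
- Rescue 80% and 40%, q = 30%: 31.6% versus 20.8%; difference 0.9 × 0.3 × (0.4 − 0.8) = −10.8 points.
- Equal rescue, 40% and 40%: 0 points for any q.
- Reversed rescue, 20% placebo and 40% active, q = 10% to 30%: +1.8 to +5.4 points.
- Wider assumptions, 60% and 20%, q = 50%: 0.9 × 0.5 × (0.2 − 0.6) = −18.0 points.

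**Sensitivity to background.** With b = 20%, the first two results become −1.6 and −9.6 points, because more rescued subjects would already be counted.

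**Head counts.** Expected subjects with an injection-related event in the first two scenarios: placebo 5 × 0.4 × 0.1 = 0.2 to 5 × 0.8 × 0.3 = 1.2; each active arm 15 × 0.2 × 0.1 = 0.3 to 15 × 0.4 × 0.3 = 1.8.

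**Person-time.** The share of a rescued subject's follow-up that falls after rescue, taking the last dose to be on the rescue day:
- Rescue on Day 29: (113 − 29)/113 = 74% if followed to Day 113; 30/(29 + 30) = 51% if only the 30-day window applies.
- Rescue on Day 57: (113 − 57)/113 = 50%; 30/(57 + 30) = 34%.

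Which column applies is unclear. Section 4.2.2 asks for end-of-study assessments when treatment is permanently stopped, Section 4.2.3 asks for end-of-treatment evaluations at treatment failure, and Section 5.8.2 prohibits anti-VEGF in the study eye through end of study without mentioning rescue.

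**The case against.** Counting every event after first dose is a conventional and conservative safety rule. It keeps late or residual drug effects, so treating safety differently from efficacy is not in itself an error. Safety is descriptive, with no testing (Section 7.9.4). In a study of 35 subjects, a reader can combine the listing, the by-eye tables, the causality tables and the recorded concomitant procedures to see which events followed an injection. Section 7.9 also leaves data conventions to the SAP, where a split could be set; none appears in the document under review.

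Most of this stands as mitigation, but it does not undo the pooling. Causality is classed only as related or unrelated to study drug (Section 6.2.2.5). Attribution to a study procedure is collected (Section 6.2.2.3), but rescue injection is not a named category and no table by procedure is planned. By-eye tables cannot separate drug from injection within the injected eye.

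Three stronger readings are tempting and not supported:
- **That events are charged to the randomised arm.** Section 7.5 groups the safety set by treatment actually received. The two normally agree, and rescue creates no new group.
- **That the tables will be biased in favour of MT-0814.** That requires more rescue on placebo, which is an assumption. Nor does the Section 1.3 remark, which concerns lifetime dosing, support any particular event rate over a few weeks.
- **That the comparative tables should simply stop at rescue.** Rescue follows ocular worsening, so that cut-off is informative, and it would drop delayed drug effects in the subjects doing worst. After early rescue the lost follow-up is not small, as the Day 29 figures show.

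**Conclusion.** The point holds as a gap in the planned displays. The treatment-emergent window is open-ended, collection can run past rescue, and no table separates what happened under study drug from what happened after an injection.

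The size is conditional. It is about 2 to 11 points in any-ocular-event incidence under the main assumed rates with 10% background risk, up to 18 under wider ones, zero with equal rescue, and of opposite sign if MT-0814 is rescued more. On the placebo arm, 1.8 to 10.8 points is 1.8/20 = 0.09 to 10.8/20 = 0.54 of one subject. The practical exposure is therefore a single event moving that column by 20 points without the table showing whether it followed an injection. This is a cheap improvement worth making; it does not show that the planned safety summary is invalid.

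**What to change.** - Keep the planned all-event tables unchanged.
- Add a supplementary table of study-eye ocular events with onset before the first rescue injection, giving subjects with events and events per 100 person-years, with person-time censored at that injection.
- Add a separate table of study-eye ocular events with onset after rescue, by original study treatment. State in advance how an event with onset on the injection day is assigned.
- Reconcile Sections 4.2.2, 4.2.3 and 5.8.2 on how long rescued subjects are followed and which visit's assessments apply, since this sets how much time after rescue is counted.

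The cost is one date flag, already needed for the time-to-rescue endpoint, and two short tables. The downside is that the pre-rescue table is subject to informative censoring, and its percentages will tend to be lower where rescue comes earlier simply because follow-up is shorter. It must be read beside the all-event table and not replace it.

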### **7.9.4.2 Physical Examinations**

Abnormal physical examination findings will be listed.

### **7.9.4.3 Vital Sign Measurements**

Observed values for vital sign measurements at Baseline and Weeks 4, 8, 12 (EOT), and 16 (EOS) — as well as changes from Baseline to postbaseline values in vital sign measurements — will be summarized descriptively by treatment group. All vital sign measurement data will be listed.

### **7.9.4.4 Clinical Laboratory Tests**

Observed values for clinical laboratory tests (hematology, serum chemistry, and urinalysis) at Screening, Weeks 4 and 8 (serum chemistry only), Week 12 (EOT), and Week 16 (EOS) will be summarized descriptively by treatment group. Additionally, shift tables will be presented for all clinical laboratory test parameters from Screening to Week 12 (EOT) and Week 16 (EOS), and for serum chemistry test parameters from Screening to Week 4 and Week 8. All clinical laboratory test data will be listed.

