		
Rationale — Technical oversight.
 
13. Clinical Laboratory Tests (Section 6.2.3): Urine Drug Test and Schedules of Study Events (Table 13–1): Urine Drug Test
 
Change — Revised to indicate that urine drug tests will be performed at Screening and on Day 1.
 
Rationale — Typographical error.
 
14. Statistical and Analytical Plan: Description of Subgroups to be Analyzed (Section 7.6)
 
Change — Revised to include an efficacy subgroup analysis for the presence versus absence of RAP.
 
Rationale — Technical oversight.
 
15. Statistical and Analytical Plan: Subject Demographics and Other Baseline Characteristics (Section 7.7) and Treatment Exposure and Compliance (Section 7.8)
 
Change — Revised to clarify that these analyses will be performed for the full analysis set, the per-protocol set, and the safety set of the study’s subjects.
 
Rationale — Technical oversight.
 
16. Statistical and Analytical Plan: Clinical Laboratory Tests (Section 7.9.4.4); Schedules of Study Events (Table 13–1): Serum Chemistry
 
Change — Revised to include serum chemistry tests and analyses at Week 4 and Week 8.
 
Rationale — Revised per United States Food and Drug Administration (FDA) non-hold comments for Investigational New Drug [REDACTED]

		
17. Schedules of Study Events (Table 13–1): Physical Exam, Medical/Medication History
 
Change — Revised to include this event on Day 1.
 
Rationale — Typographical error.
 
18. Schedule of Study Events (Table 13–1)
 
Change — Three additional rows were added to the end of the table, indicating the following events on the study schedule: “study drug dispensed,” “concomitant medications reviewed,” and “subject diary reviewed.”
 
Rationale — Technical oversight.

3.0	27 June 2019	Amendment 2

Version Number	Approval Date	Summary of Changes

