		
6. Safety Analyses: Schedules of Study Events (Table 13–1): Serum Chemistry
 
Change — Revised to include the collection of additional serum chemistry samples at Weeks 0, 1, 2, 3, 5, 6, 7, 9, 10, and 11.
 
Rationale — Revised per safety review committee meeting discussion.
 
7. Slit-Lamp Biomicroscopy (Section 7.9.4.6)
 
Change — Revised to exclude lens opacity assessments obtained via LOCS III for ocular findings.
 
Rationale — Revised as lens opacity assessments will not be evaluated using normal/abnormal categories.

		
8. Minor corrections and clarifications
 
Change — The amendment also includes additional minor clarifications and corrections.
 
Rationale — Minor corrections and clarifications are included in the revised text for consistency.

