### 13 Schedules of Study Events

**Table 13–1 Schedule of Study Drug Administration, Examinations, and Observations**

Visit No.	1	2 a (RAN/ SOT)	3	4	5	6	7	8	9	10	11	12	13	14 b (EOT)	15	16	17	18 c (EOS)
Study Week	-2	0	1	2	3	4	5	6	7	8	9	10	11	12	13	14	15	16
Study Day: (Allowance):	≤14 Days Before Day 1	1	8 (±2)	15 (±2)	22 (±2)	29 (±2)	36 (±2)	43 (±2)	50 (±2)	57 (±2)	64 (±2)	71 (±2)	78 (±2)	85 (±2)	92 (±2)	99 (±2)	106 (±2)	113 (±2)
Informed Consent	X																	
Demographics	X																	
Eligibility (Inclusion/Exclusion Criteria)	X	X																
Study Drug Administration		X	→ X i															
ETDRS BCVA d	X	X	X	X	X	X	X	X	X	X	X	X	X	X	X	X	X	X
Optical Coherence Tomography d,e	X	X	X	X	X	X	X	X	X	X	X	X	X	X	X	X	X	X
Slit Lamp Biomicroscopy d	X	X	X	X	X	X	X	X	X	X	X	X	X	X	X	X	X	X
Intraocular Pressure d	X	X	X	X	X	X	X	X	X	X	X	X	X	X	X	X	X	X
Color Fundus Photography d	X		X	X	X	X	X	X	X	X	X	X	X	X	X	X	X	X
FA/ICGA Screening f	X													X				
Vital Signs g	X	X				X				X				X				X
Physical Exam, Medical/Medication History	X	X												X				X

Visit No.	1	2 a (RAN/ SOT)	3	4	5	6	7	8	9	10	11	12	13	14 b (EOT)	15	16	17	18 c (EOS)
Study Week	-2	0	1	2	3	4	5	6	7	8	9	10	11	12	13	14	15	16
Study Day: (Allowance):	≤14 Days Before Day 1	1	8 (±2)	15 (±2)	22 (±2)	29 (±2)	36 (±2)	43 (±2)	50 (±2)	57 (±2)	64 (±2)	71 (±2)	78 (±2)	85 (±2)	92 (±2)	99 (±2)	106 (±2)	113 (±2)
Electrocardiogram	X													X				
Hematology	X													X				X
Serum Chemistry	X	X	X	X	X	X	X	X	X	X	X	X	X	X				X
Urinalysis	X													X				X
Plasma Concentration Analysis Sampling h		X				X				X				X				
Serum Pregnancy Test i	X																	X
Urine Dipstick Pregnancy Test i		X																
Urine Drug Test	X	X																
Study drug dispensed		X				X				X								
Concomitant medications reviewed		X	X	X	X	X	X	X	X	X	X	X	X	X	X	X	X	X
Subject diary reviewed			X	X	X	X	X	X	X	X	X	X	X	X				
Adverse Events	X	X	X	X	X	X	X	X	X	X	X	X	X	X	X	X	X	X

Abbreviations: BCVA = best-corrected visual acuity; [REDACTED] EOS = end of study; EOT = end of treatment; ETDRS = Early Treatment of Diabetic Retinopathy Study; FA = fluorescein angiography; ICGA = indocyanine green angiography; OCT = optical coherence tomography; [REDACTED] RAN = randomization; SOT = start of treatment.

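### Section 7.9.4.4 names by-arm serum chemistry summaries at 5 of the 15 visits in Table 13–1, and its glucose and triglyceride shifts start from a Screening sample that need not be fasting

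*Combined protocol and SAP*

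**What the plan says.** The row "Serum Chemistry" in Table 13–1 is marked at Visits 1 to 14 and at Visit 18. Section 7.9.4.4 then sets out three things:

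- **Summaries by treatment group:** "Observed values for clinical laboratory tests (hematology, serum chemistry, and urinalysis) at Screening, Weeks 4 and 8 (serum chemistry only), Week 12 (EOT". The list closes with Week 16.
- **Shift tables:** for all laboratory parameters from Screening to Weeks 12 and 16, "and for serum chemistry test parameters from Screening to Week 4 and Week 8".
- **Listings:** "All clinical laboratory test data will be listed".

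Section 7.9.4 says generally that safety data, including laboratory tests, are summarised and listed without hypothesis testing. Section 7.9 leaves details to an SAP; no separate SAP text is among the documents.

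Section 6.2.3 does not require fasting at Screening but requires an 8-hour fast before every later laboratory visit.

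The amendment history is context only. Amendment 1 (item 16) names "Statistical and Analytical Plan: Clinical Laboratory Tests (Section 7.9.4.4") among the places changed, and its entry reads "Revised to include serum chemistry tests and analyses at" Weeks 4 and 8. Amendment 3 (item 6) reads "Revised to include the collection of additional serum chemistry samples at Weeks 0, 1, 2, 3, 5, 6, 7, 9, 10, and 11", with the reason "Revised per safety review committee meeting discussion".

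**The concern.** Two current parts of the protocol do not match: the sampling schedule is weekly during treatment, while the by-arm chemistry tables are named at four-week steps. Safety is part of the primary objective in Section 2.1, Section 1.3 describes the drug's human safety profile as limited, and the added samples followed a safety committee discussion. If Section 7.9.4.4 is followed literally, a modest or transient chemistry change confined to Weeks 1–3, 5–7 or 9–11, and not judged clinically significant by an investigator, would be visible only in listings. Listings do not show readily whether a pattern differs by arm or over time.

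The shift tables raise a second, smaller issue. If a subject has eaten before the Screening draw, a glucose or triglyceride shift compares a fed value with a fasting one. A raised fed value at Screening could hide a later rise, or produce an apparent fall.

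**Working it through.** **Visit count.** Inputs are the serum chemistry row of Table 13–1 and the visit list in Section 7.9.4.4.

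| | Visits | Count |
|---|---|---|
| Scheduled | Screening (1) + Weeks 0–12 (13) + Week 16 (1) | 15 |
| Named for by-arm summary | Screening, Weeks 4, 8, 12, 16 | 5 |
| Not named | Weeks 0, 1, 2, 3, 5, 6, 7, 9, 10, 11 | 10 |

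After Day 1 there are 12 + 1 = 13 scheduled chemistry visits (Weeks 1–12 and 16). Four are named and 9 are not. The ten unnamed visits are exactly those listed in Amendment 3.

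**Comparison within Section 7.9.4.** The hematology and urinalysis summaries match their schedule (Screening, Weeks 12 and 16). Vital signs (7.9.4.3) are summarised at their scheduled visits from Baseline on. Intraocular pressure, also measured weekly, is summarised at each visit (7.9.4.7). Weekly slit-lamp findings feed a shift to the worst postbaseline result (7.9.4.6). Among these measures, only serum chemistry has weekly treatment-period data that enter neither kind of named table.

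**Samples affected.** The documents do not say how many subjects followed version 4.0. Assume that n of the 35 planned subjects followed it in full, and that the other 35 − n had postbaseline chemistry only at Weeks 4, 8, 12 and 16. Then unnamed samples = 9n, and all postbaseline samples = 13n + 4(35 − n).

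| n | Unnamed / all | Share |
|---|---|---|
| 0 | 0 / 140 | 0% |
| 10 | 90 / (130 + 100) = 90 / 230 | 39% |
| 20 | 180 / (260 + 60) = 180 / 320 | 56% |
| 35 | 315 / 455 | 69% |

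The range runs from none to 315. Early end-of-treatment evaluations after treatment failure (Section 4.2.3), or withdrawals, would lower the counts. Subjects who changed version during treatment are not modelled. The shares count samples without a named table; they do not measure bias or missed signals.

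**Shift reference.** All four chemistry shift targets (Weeks 4, 8, 12, 16) start from Screening. The start may be fed or fasting; the end must be fasting. Section 6.2.3 lists 27 chemistry analytes, counting HDL and LDL, and total and direct bilirubin, separately. The section itself flags glucose; adding triglycerides is my judgement. That gives 2 of 27. The number of subjects not fasting at Screening is not stated.

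**Is Day 1 a usable baseline?** A chemistry sample is now scheduled on Day 1, after an 8-hour fast. However, the first dose is given at that same visit (Table 13–1, footnote a), and a predose draw is specified only for plasma concentration samples (Section 6.4, Table 13–2). Day 1 is therefore a valid pre-treatment reference only where the record shows that the draw preceded the dose.

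**The case against.** The strongest reply is that little is lost. All laboratory results are listed. Results judged clinically significant become adverse events (Section 6.2.9), apart from those tied to the underlying disease and no worse than expected, and treatment-emergent events are summarised by arm (7.9.4.1). Section 7.9.4 already promises summaries of safety data, the SAP may supply the visits, and a collection schedule need not equal a table schedule. These points stand and limit the size of the finding. They do not close the gap, because Section 7.9.4.4 gives an explicit visit list and no supplied text extends it.

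A reader might infer that Amendment 3 simply forgot to update Section 7.9.4.4. The contrast between the two amendment entries suggests this but does not establish it: the Amendment 3 item is itself headed as concerning safety analyses, and intent is nowhere stated. The mismatch rests on the two current passages, not on the log.

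A reader might also conclude that all chemistry shifts should move to Day 1. That goes too far. Screening is the one chemistry sample that is certain to precede dosing and is shared with hematology and urinalysis, which have no Day 1 sample. Fasting status does not justify replacing it for the other 25 analytes.

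A shift to the worst postbaseline chemistry value is tempting too, but sample counts may differ between subjects. If each sample independently has probability p of being out of range, the chance of at least one in k samples is 1 − (1 − p)^k. For p = 1%, 2.5% and 5% (assumed), this is 3.9%, 9.6% and 18.5% with 4 samples, against 12.2%, 28.0% and 48.7% with 13. With 5 planned placebo subjects, a chance imbalance in protocol version could show up as an arm difference.

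**Conclusion.** The point holds in a limited form. Ten of the 15 scheduled chemistry visits, 9 of the 13 after Day 1, have no by-arm summary named in Section 7.9.4.4 and are assured only in listings. Separately, glucose and triglyceride shifts may compare a fed Screening value with a fasting one. The visit count is firm; the number of samples and subjects affected cannot be determined from the documents.

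The consequence is confined to descriptive safety reporting. No efficacy result changes, no safety test is planned, and the by-arm observed values at Weeks 4, 8, 12 and 16 are fasting and do not depend on Screening. Nothing supports saying that the weekly data are discarded or that the shift tables as a whole are invalid. The conclusion concerns the protocol text; an SAP that names the extra visits would settle the first part. This is a worthwhile, inexpensive correction.

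**What to change.** In Section 7.9.4.4 and the SAP:

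1. Summarise serum chemistry by arm at every visit scheduled in Table 13–1, showing n at each visit because not all subjects may have followed version 4.0. If the shorter list was intended, say so and give the reason.
2. Keep Screening as the shift reference for all other analytes. For glucose and triglycerides only, take the shifts from the fasting Day 1 sample where it is documented as drawn before the first dose; otherwise use Screening and flag the subject.

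A worst-postbaseline chemistry shift is optional and not part of this finding. If used, it should account for the unequal number of samples per subject.

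The cost is table programming on samples already scheduled, with no new visits, plus a check that draw and dose times on Day 1 were recorded. It can be done before the SAP is signed and the database locked (Section 8). The drawbacks are extra descriptive tables, small n at some visits, and a mixed baseline source for two analytes.
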